further for eligibility using the participant eligibility summary (PES). Eligible participants will undergo informed consent procedures and a total of 60 participants will be randomized to the collaborative care intervention (n = 30) or care as usual (n =30) condition. Intervention activity will continue for three months after the ED visit, while follow-up continues for six months after the ED visit. Primary outcomes include feasibility. Secondary outcomes include substance use measured by days of use of opioids as well as utilization of healthcare services including ED visits, primary care visits, mental health visits and substance use treatment visits.

1. Aims and Hypotheses

- 1) The primary aim** of the investigation is to determine the feasibility of the collaborative care intervention initiated from the ED and delivered longitudinally. Taken together, all elements of the intervention are referred to as ED-LINC. Feasibility measures include enrollment rates, retention rates at each outcome and follow-up assessment, intervention completion rates and number and types of contacts made by the interventionist. Feasibility of implementation will also be assessed. Guided by Proctor's taxonomy of implementation outcomes⁷, acceptability, feasibility and fidelity to ED-LINC will be measured.
- 2) The secondary aims** of the study are to determine differences in substance use and health care utilization between the two arms. While the study is not powered to detect a difference as this is a feasibility pilot study, substance use and health care utilization will be measured. Specifically, substance use will be measured utilizing a time-line follow back calendar administered by the research assistant to determine days of heroin or illicit opioid use and days of prescription opioid misuse. Additionally, EDIE will be utilized to determine ED utilization and inpatient admissions across Washington, Oregon, Alaska and other areas that EDIE is active. Participants will provide self-report information on primary care visits, mental health and substance use treatment visits. Engagement in substance use treatment will be confirmed via phone by study staff at all periods of assessment.

2. Participants

a. Inclusion Criteria:

- Aged 18-65
- Patients with at least one risk factor for opioid use disorder via the EMR pre-screen

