The study research coordinator (RC) will be trained in delivering evidence-based Motivational Interviewing (MI). There is a large body of evidence that supports the use effectiveness of motivational interviewing from the ED for patients with substance use^{3,11-14} using the Screening Brief Intervention and Referral to Treatment (SBIRT) framework. However, SBIRT is not effective in decreasing problematic drug use when used alone.¹⁵ During ED-LINC, the research coordinator will perform a brief negotiated interview (BNI) with a goal of increasing motivation to link to outpatient services including

primary care and/or outpatient substance use services. It is expected that the BNI will last 10-15 minutes and the RC will record the length in minutes of each session in RedCap. Important steps to the BNI include; 1) raising the subject 2) providing information and feedback 3) enhancing motivation 4) development of an action plan. The RC will build rapport through non-judgmental active listening and affirming patient strengths and values through complex reflections.

- 1) Raising the subject/Building Rapport
 - Establish rapport through non-judgmental active listening
 - Ask permission to discuss substance use
- 2) Providing feedback
 - Ask about the patient's frequency and pattern of drug use
 - Review screening results
 - Ask about connection between substance use and health (if applicable)
 - Provide information about substance use treatments and referrals
- 3) Enhancing motivation
 - Evoke change talk with MI techniques such: the readiness ruler, assessing pros and cons
 - Use opened ended questions, affirmations, reflections, and summaries (OARS).
 - Emphasize personal autonomy and responsibility
- 4) Negotiate a plan
 - Negotiate a goal for use and/or treatment engagement
 - Provide thoughts with permission
 - Discuss details for a follow up meeting

A procedural checklist will be used by the RC to document process fidelity to the BNI. (See Appendix A).

Pharmacotherapy

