
Longitudinal Care Management

Participants will be followed by the study team for care management for three months. During the initial recruitment interview, the RC will ask the participant about preferences and schedule ongoing times to communicate based on participant preferences. All participants will be contacted by the RC within 3-4 days of enrollment by the preferred method of contact (e.g. text, call) to check-in. Participants who received buprenorphine will receive a phone call within 24 hours by a member of the study team. The RC will

work with the study participant to establish with a new primary care provider, or schedule and attend a follow-up appointment with their existing primary care provider.

Additionally, tailored to each participant, the RC will work to actively connect participants to substance use treatment and community mental health providers. Previously care management tasks included coordinating care with existing providers, providing referral and information for housing, managing care for substance use, meeting participants during subsequent HMC ED or outpatient visits to check-in and accompany participants to HMC appointments as needed.⁹ Care management tasks will be logged and tracked in RedCap by the RC and other members of the study team.

Care Plan

During the initial recruitment, participants will be notified that a Care Plan will be placed in the Emergency Department Information Exchange (EDIE). The Emergency Department Information Exchange (EDIE) system allows team members to implement electronic health care record innovations, such as the creation of care plan notifications that provide the care team contact information for the study team which can be viewed across emergency department sites utilizing the system. EDIE also provides real-time work-flow integrated electronic alerts that allow collaborative team providers to be notified when patients make recurrent visits to an emergency department in the state of Washington and Oregon. Care Plans in EDIE are used as standard of care at HMC and the care plan for ED-LINC was adapted from existing projects (See Appendix B)

Weekly Supervision and Case Conference

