Consistent with the guidelines of collaborative care, the RC will receive supervision from the study physicians. The study PI, [name] and study psychiatrist, [name] will be available to discuss all new ED-LINC participants at the time of enrollment and regularly scheduled supervisory meetings will be held with all study team members weekly to every-other week depending on case load and availability. During these meetings, the RC will lead a discussion of all newly enrolled participants as well as any active participants. A discussion of relevant assessments will take place for all discussed participants to tailor further care management and linkage to services. Content of these discussions will be documented in RedCap. All members of the team attending the supervision and case conference meetings will have obtained human subjects training prior to participating.

Cell Phone

The study [contact]) will be provided to all participants in the ED-LINC intervention. Specifically, after the baseline interview participants randomized to ED-LINC will be provided with the cell phone number and notified that they can call or text this number with any concerns during the course of their intervention time. The cell phone will be covered by the study RA/RC or study PI from 9a-5p M-F and by one of the study physicians on evenings, nights and all day weekends and holidays. All efforts will be made to answer the call during business hours and response to calls and text during business hours will be within 1-2 hours. Efforts will be made to be timely after hours as well. Participants will be notified that calls and texts that occur after hours, on weekends and on holidays can be anticipated to be answered within 24 hours. All interactions with participants on the study cell will be tracked in research logs and notes captured in RedCap.

H. Intervention Training and Supervision

1. Training

The study research assistant will receive training in Motivational Interviewing in order to perform the Brief Negotiated Interview (BNI) with fidelity. Specifically the RA will attend a 1-day workshop specific to Motivational Interviewing techniques in substance use and will complete practice sessions (e.g. standardized patients) and receive feedback on the core principles of BNI. The RA will receive at least 16 hours of training which is consistent with other studies conducting similar interventions.

2. Supervision

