The baseline and follow-up study assessments for collecting patient-reported outcomes (PRO) may be completed using various methods. PRO data will typically be obtained from the patient during in person or telephone interviews with a study team member (e.g., research coordinator or research assistant). The study team member will log in via user name and password to the REDCap web-based platform on a computer on the secure UW Medicine server or log in via user name and password to the REDCap application on an encrypted iPad. Participants will also have the option of receiving an email link to the survey questions to complete follow-up interviews on their own directly in to the encrypted REDCap web-based platform. If a participant has received the email link from the study team they do not need a REDCap user name or login in order to access and complete the survey.

The study team could also use a hard copy paper version of the assessment to be completed by an interviewer in the hospital or convenient location, or the hard copy interview could be mailed or faxed directly to participants for them to fill in own their own and return in a pre-paid, self-addressed envelope.

After receiving the hard copy interview back in the a member of the study team would then enter the responses from the hard copy or PDF into REDCap. Data collected in a hard format (e.g., on paper) will be stored in a locked cabinet in locked study office space. Regardless of the data collection method, interview responses will not be labeled with directly identifying information; instead, they will be labeled with the participant's study ID number to maintain confidentiality. As mentioned above, all data stored in REDCap is encrypted and safe-guarded behind firewalls.

4. ED-LINC Intervention and Usual Care (UC) Delivery Documentation

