Data collected about the process of care, including ED-LINC intervention care management notes and UC documentation will be obtained from encounters with the patient or their providers, or from the EMR or EDIE, and entered directly into REDCap. Due to the nature of these encounters, the data related to the intervention may contain identifying information or may have identifying information piped in or linked from the patient contact form (e.g., patient name, birthdate, address) and the provider contact form (e.g., provider name, position, phone number) within the project. Intervention specific logging will be accessible only to members of the intervention team granted permission by the PI in order to maintain the blinding of the follow-up interview team.

If limited by technological constraints, intervention study team members may need to take hard copy notes from encounters for subsequent entry into REDCap. As these hard copy intervention notes may contain identifiable information, they would be stored in a locked office or filing cabinet, separate from participant's de-identified study data.

5. Emergency Department Information Exchange (EDIE)

Collective Medical Technologies (CMT) owns and manages EDIE, which collects health care utilization data including emergency department utilization data for patients across WA and OR state. The CMT servers, networks, and databases that house and transmit EDIE data are co-located in certified Data Centers with fully redundant systems and 24/7/365 security monitoring. CMT Data Centers are certified

in, or have been audited against the following: SOC I, SOC II Type II and SOC III reporting; ISO/IEC 27000 Series; NIST 800-53; ITIL 3.0; HIPAA Privacy and Security & HITECH Rules; and Gramm-Leach-Bliley Act (GLBA) Interagency Guidelines.

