REDCap data quality will be monitored periodically by the study PI and/or data analyst. In the event that any changes need to be made to the data, these changes will be made directly in REDCap. There is a data logging tool in REDCap that allows administrators to track changes to the project. This tool provides access to an audit trail created by REDCap. For each entry that changes data in the database, REDCap records the date, time, username of the person logged in at that time, the type of event and the changes that were made. This audit trail in the data logging tool stores every entry/change throughout the life of the database. Specific checks for completion and accuracy are outlined below for the primary and secondary outcomes and for intervention and usual care activity. Certain patient-reported outcomes (PRO) will be used in the 'Anticipated AE/SAE' log as well. Specifically, PRO's on suicide and overdose will be reviewed as described above.

- Feasibility**

Feasibility measures include enrollment rates, retention rates at each outcome and followup assessment, intervention completion rates and number and types of contacts made by the interventionist. At team meetings, the CONSORT diagram will indicate enrollment and retention rates. At least monthly, the study RA/RC and PI will review the ED-LINC contact log in RedCap for completeness, accuracy and content. Feasibility of implementation will also be assessed using specific assessments of ED-LINC participants at the 6-month follow-up visit. The rates of completion of these assessments will be assessed.

- Substance Use and TLFB**

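### The Protocol says follow-up interviewers are blinded, but its own role assignments contradict this and no stated procedure secures it

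*Protocol*

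**What the plan says.** **The claim and its safeguard.** Protocol VI.B.4 (intervention and usual care delivery documentation) states: "Intervention specific logging will be accessible only to members of the intervention team granted permission by the PI". The purpose given is "in order to maintain the blinding of the follow-up interview team". Neither document describes any other measure to keep interviewers blind.

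**Who delivers ED-LINC.** In III.G (Brief Negotiated Interview), "the research coordinator will perform a brief negotiated interview (BNI", the bedside component of ED-LINC. III.H.1 gives the same task to another post: "The study research assistant will receive training in Motivational Interviewing in order to perform the Brief Negotiated Interview (BNI) with fidelity". On the three months of follow-on work, III.G (Longitudinal Care Management) says: "Care management tasks will be logged and tracked in RedCap by the RC and other members of the study team".

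**Who collects outcomes.** In II.B.1, substance use is measured with a "time-line follow back calendar administered by the research assistant". VI.B.3 says patient-reported outcomes will typically come from in-person or "telephone interviews with a study team member (e.g., research coordinator or research assistant").

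**What is asked at 6 months.** VII.B.2 (Feasibility) measures implementation through "specific assessments of ED-LINC participants at the 6-month follow-up visit". The SAP (Primary Outcome Measures) likewise gives the Implementation Appropriateness measure to the ED-LINC arm only.

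**The concern.** A blinding statement tells readers that the person eliciting self-reported outcomes did not know the arm, and so could not have let that knowledge affect questioning, probing or coding. If the statement is carried into a report while the same posts both treat and assess, the report claims a protection that the procedures do not provide.

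Two outcomes depend on it most, because they are self-reports usually collected by interview and compared between arms:

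- TLFB days of opioid use, the SAP's listed secondary outcome, which is modelled with the intervention as a term.
- Perception of care coordination, listed in the SAP as a primary outcome and compared between groups with a Wilcoxon rank sum test.

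On the role assignments as written, an ED-LINC participant could be asked about opioid use, or about how well care was coordinated, by someone who took part in coordinating it. A usual-care participant has no such relationship with the interviewer.

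**Working it through.** No sample size, power or error-rate figure bears on this point. The check sets the sections on delivery, assessment and log access side by side.

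**Step 1. Compare the roles.**

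| Post | Part in ED-LINC | Part in outcome collection |
|---|---|---|
| Research assistant (RA) | Trained to perform the brief negotiated interview (III.H.1); supervised in the weekly ED-LINC case conference (III.H.2); shares weekday cover of the ED-LINC phone (III.G, Cell Phone) | Administers TLFB (II.B.1); example of an interviewer (VI.B.3) |
| Research coordinator (RC) | Performs the brief negotiated interview and care management (III.G); leads case discussion (III.G, Weekly Supervision); shares phone cover | Example of an interviewer (VI.B.3) |

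Both posts appear in both columns. The RA row is the stronger one, because II.B.1 assigns TLFB to the RA outright. The RC is placed in follow-up interviews only by way of example.

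**Step 2. Test the safeguard.** VI.B.4 relies on keeping the intervention log from interviewers. VII.B.2 (Feasibility) has the RA/RC and the principal investigator review the ED-LINC contact log at least monthly. So the post assigned to TLFB also reads ED-LINC logging, and the restriction does not cover it.

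**Step 3. The 6-month visit.** Assessments meant for one arm disclose that arm to whoever administers them. Neither document says whether TLFB comes before or after them. If TLFB comes first, that TLFB is unaffected by this route; if it comes after, it is not. This route does not arise at the 1- and 3-month interviews, where the problem is the role overlap and log access.

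The scale of this route follows from the planned numbers. At the 80% retention in II.B.3, 0.80 × 20 = 16 ED-LINC interviews would be held at 6 months with the SAP's 20 per arm, or 0.80 × 30 = 24 with the Protocol's 30. These are ceilings on expected interviews: self-completed interviews, and those with TLFB asked first, drop out of the count.

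**Step 4. Other ways an interviewer can learn the arm.**

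- Participants are told their assignment (III.D) and may mention it.
- The enrollment log holds the assignment (VI.B.2).
- The follow-up team may look in EDIE for contact details (III.I), and the sample care plan placed there identifies the patient as being in ED-LINC (Appendix B).

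**Step 5. Look for a rule or check that closes the gap.** Neither document requires that a participant's interviewer be someone who did not treat that participant, and neither plans to record or test whether interviewers knew the arm.

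**The case against.** The strongest reply is that the overlap is in job titles, not people. The Protocol often writes as if there were separate groups: a follow-up team (III.I), care managers and follow-up interviewers listed as different staff (IV.D.5), an intervention team distinct from the interview team (VI.B.4), and follow-up interviewers who hand off to a clinical team (Appendix C). This stands. Separate staff may well have been intended, and the documents do not show that any participant was interviewed by the person who treated them. But intention is not procedure, and the RA's listed duties run against it.

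Three stronger readings are tempting, and the documents do not support them:

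- *That every ED-LINC interview at 6 months is unblinded.* About 20% attrition is expected, interviews may be self-completed (III, Follow-up Interviews; VI.B.3), and TLFB may come first. The SAP also calls Implementation Appropriateness a self-report measure without saying that an interviewer gives it.
- *That the bias has a known size or must favour ED-LINC.* Under-reporting to a care manager is plausible, but usual-care participants may under-report too. The documents give nothing from which to derive a size or direction.
- *That blinding interviewers would remove the problem.* Participants know their arm (III.D), so their own response bias would remain.

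Satisfaction is a weaker example than the two outcomes named above: the SAP describes a questionnaire that each participant completes, and it may not pass through an interviewer.

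It is also fair to say that this is a feasibility pilot, stated in II.B.1 not to be powered for between-arm differences. Refusal and follow-up completion are counts that hardly depend on who asks the questions. This limits the consequence but does not make the blinding statement accurate.

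**Conclusion.** The point holds as a contradiction between a stated property and the plan's own assignments: blinding is claimed, the single safeguard does not cover the post that collects TLFB, and no rule separates deliverers from assessors. This goes beyond missing detail. It would be too strong to conclude that blinding actually failed, since that depends on who filled the posts, and staffing records could show separation.

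What is at stake is how far the between-arm comparisons of TLFB days and perception of care coordination can be described as blind-assessed. No numerical effect on either can be stated. The conclusion rests on reading RA and RC in the delivery sections as the same posts named in the assessment sections. It deserves correction but does not threaten the main feasibility counts.

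**What to change.** With existing staff:

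1. State in VI.B.4 that, where staffing allows, nobody who delivered ED-LINC to a participant, or who has access to the ED-LINC log, collects that participant's follow-up outcomes. Bring II.B.1, III.H, VI.B.3 and VII.B.2 into line.
2. At 6 months, complete TLFB and all common items before the ED-LINC-only items, or have those items self-completed. The e-mail link in VI.B.3 is one route, but e-mail is not a required contact detail (III.I), so the mailed or faxed paper form is needed as well.
3. Add a REDCap field at each interview recording whether the interviewer knew the arm.

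If the first item is not or was not met, delete the blinding statement in VI.B.4 and report outcome assessment as unblinded. This applies if RA and RC are in practice one post. It also applies if data collection is already finished, as the September 2021 SAP's partly past-tense wording suggests, unless staffing records show separation.

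The cost is a small change to the rota and form order plus one data field, or else a less favourable but accurate statement.

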Appendix A

BI Evaluation Sheet

Did the provider				What did the provider do?	How did the client respond
Raise Subject	
 • Establish rapport? • Respectfully ask permission to discuss substance use • Ask for description of substance use patterns? 	Yes	No		
Provide Feedback	
 • Ask about connection between substance use & health issues (if any)? • Review screening results? • Compare results to national norms? • Review low risk guidelines? • Express professional concern? 	Yes	No		
Enhance Motivation	
 • Review pros and cons of use? • Use a scaling question (ruler) to elicit arguments for positive change? • Emphasize personal responsibility? 	Yes	No		

Negotiate Plan	
 • Elicit change plan by asking about next steps? • Summarize? • Re-state professional recommendation? 	Yes	No			
To what degree did the clinician use a Motivational Interviewing style?						
Self-evaluation of the BI session focusing on strong points, skills to work on, and observations about the entire SBIRT process.						

